			
8.2.3.1.3. Analisis of deaths
 

• Added SMR

 
CCI [REDACTED] [REDACTED]
 
8.2.3.2. Safety analysis in the Xeljanz group
 

• Added some diseases for current analyses.

 
CCI [REDACTED] [REDACTED]
 
9. Listings
 

• Added list of contraindicated patients with adverse drug reactions.

 
10. References
 

• Added some references.

 
11.1.3. Patient Background Considered for Safety
 

• Deleted organization that established the hospital.

 
11.1.5. Numbers of patients with malignant tumors in reference population (2013)
 

• Deleted this section.

 
Refined typos were corrected, and presentation and wording.

10.0	06/DEC/2021	PPD	
After the database was released, it was found that the handling of the death cases was not appropriate, so the following sections were corrected.
 
6.1.1. Comparison of Xeljanz group and control group
 

• Changed the handling of death cases.

 
7. Handling of Missing data
 

• When comparing the xeljanz group and the control group, the conditions to include as death cases were added.

## 2. INTRODUCTION

This statistical analysis plan describes the statistical analysis plan for the special investigation of Xeljanz Tablets 5 mg (A3921194). In this plan, texts cited from the protocol are shown in *italics*.

### 2.1. Study Design

This survey is a non-interventional study that includes patients who received Xeljanz Tablets (hereinafter referred to as Xeljanz) (Xeljanz group) and patients who started medications for rheumatoid arthritis other than Xeljanz (hereinafter referred to as control drugs) (control group) among patients with uncontrolled rheumatoid arthritis despite the continued use of methotrexate (hereinafter referred to as MTX) at a dose exceeding 8 mg/week for at least 3 months in the cohort.

The control group will include Xeljanz-naive patients, and clinical trial participants are not allowed to be registered in the control group.

<Scheduled number of patients to be investigated>

*Target sample size: Subjects who meet the conditions in “2. Subjects” for each group and the sample size is shown below.*

*1) Xeljanz group: 4000 subjects for safety analysis*

The target sample size is set to be 4000 subjects by adding a certain sample size a) b) exceeding 3000 subjects beginning from the start of registration (3-year observation) to the subsequent number of subjects (6-month observation period). See “6.5 observation period” for more information. However, even if Xeljanz is administered to subjects who do not meet the conditions described in “2. Subjects” for inevitable reason(s), while such subjects will not be included in the above sample size, the request to enroll subjects and complete survey forms will be made for subjects in the Xeljanz group for the sake of all-cases survey.

*2) Control group: A certain sample size a) b) exceeding 2000 subjects for safety analysis*

*[Remarks]*

*a) The sample size in both groups will be set to be the number of subjects for whom the degree of statistical accuracy described in [Rationale for sample size] is maintainable. See the Appendix for more information.*

*b) The registration period until a certain sample size is reached will be the same period for both groups.*

<Rationale for the scheduled number of patients to be investigated>

*The incidence of malignant tumors after administration of Xeljanz in a Japanese long-term study (Study No. A3921041) is 1.16 (/100 patient-years). Since the dropout rate in clinical studies is 31% in subjects who proceeded to the Japanese long-term study (Study No. A3921041) from a Japanese phase II study (Study No. A3921039) (duration of treatment, 3 years) and 14% in subjects who proceeded from a Japanese phase II study (Study No. A3921040) (duration of treatment, 1.4 years), the dropout rate at the completion of 3-year observation under the actual use conditions in routine practice is assumed to be about 50%.*

*If the number of patients in the Xeljanz group is set at 4000, events can be confirmed in 104 patients based on the incidence of malignant tumors in Japanese patients of 1.16 (/100 patient-years).*

*Meanwhile, if the number of patients in the Xeljanz group is set at 4000 and the incidence of malignant tumors in the control group is assumed to be comparable to that in the Xeljanz group, at least 2000 patients will be required to allow a statistically valid comparison between the groups. Therefore, the number of patients in the control group was set at 2000.*

*Depending on the progress of registration, if the registered number of patients in either group significantly exceeds the above number earlier than the other group, a sample size with 3-year observation period can be changed to the combination of a sample size for whom the degree of statistical accuracy is maintainable if it is compared with 4000 patients in the Xeljanz group and 2000 patients in the control group (see the Appended Table). Also, the registration period for patients in the inter-group comparison needs to be the same.*

**<Scheduled period of the survey>**

*Duration of surveillance: From the date marketing of Xeljanz begins to the completion of assessment by regulatory authorities*

*Enrollment period: From marketing commencement for Xeljanz to clearing of approval conditions for all-cases survey*

*Completion of survey forms for the Xeljanz group will no longer be mandated upon registration of 4000 subjectsc) in the Xeljanz group, which is the target sample size, after the approval from regulatory authorities is obtained. Meanwhile, registration will be continued until the final assessment is made by regulatory authorities.*

*For the control group, both completion of survey forms and registration will no longer be mandated after the target sample size is reached and the approval from regulatory authorities is obtained.*

*\*The results of collecting and analyzing 6 months' worth of data on the 4000 subjects in the Xeljanz group will be submitted to the regulatory authorities together with the results of collection and analysis of 6 months' worth of data on the subjects in the Xeljanz group who do not meet the conditions described in "2. Subjects" and the control group.*

*c) Subjects who meet the conditions described in "2. Subjects".*

*Observation period*

*[1] Xeljanz group:*

*(1) Registered subjects up to a certain sample size exceeding 3000 subjects from the start of registration: 3 years (36 months) from the date of treatment commencement*

*(2) Registered subjects after the above (1): Only 6 months from the date of treatment commencement*

*[2] Control group: 3 years (36 months) from the date of treatment commencement*

*[3] Follow-up surveillance*

*For a period of 3 years from the date of treatment commencement, follow-up surveillance will be conducted for subjects in the Xeljanz group (1) and the control group on information related to the drug administration conditions and adverse events after discontinuation (serious infections (12 months), malignant tumors, adverse events leading to death).*

## **2.2. Study Objectives**

*This survey will be performed in patients administered Xeljanz Tablets (hereinafter referred to as Xeljanz) to obtain information on the following under the actual use conditions after marketing:*

- 1) *Development of adverse drug reactions, factors that may affect safety, and efficacy*
- 2) *Safety (malignant tumors and serious infections in particular) and efficacy in long-term use*

*The development of malignant tumors and serious infections will be compared with the control group.*

Since it has been suggested in Japanese clinical trials that Xeljanz may promote the manifestation of malignant tumors, the development of malignant tumors in the Xeljanz group will be compared with that in the control group by 3-year observation. The development of serious infections in the Xeljanz group will be compared with that in the control group by 1-year observation.

## **3. INTERIM AND FINAL ANALYSES**

In this survey, interim analyses for periodic safety update reports will be performed. Interim analyses shown in Table 1 will be performed for purposes other than periodic safety update reports.

**Table 1. Other Interim Analyses**

	Objective	Timing of implementation	Target patients
1	Safety evaluation of Xeljanz during an early post-marketing period	The timing at which 6-month data of about 500 patients in Xeljanz group are fixed.	Xeljanz group: Patients for whom at least Volume 1 is fixed at the specified timing.

**Table 1. Other Interim Analyses**

	Objective	Timing of implementation	Target patients
2	Safety evaluation of Xeljanz Safety evaluation of control group	The timing at which 6-month data of about 1000 patients in Xeljanz group are fixed.*	Xeljanz group: Patients for whom at least Volume 1 is fixed at the specified timing. Control group: patients for whom at least Volume 1 is fixed at that timing.
3	Safety evaluation of Xeljanz Safety evaluation of control group	The timing at which 6-month data of about 2000 patients in Xeljanz group are fixed.*	Xeljanz group: Patients for whom at least Volume 1 is fixed at the specified timing. Control group: patients for whom at least Volume 1 is fixed at that timing.
4	Safety evaluation of Xeljanz intended to discharge the all-cases survey.	The timing at which 6-month data in 4000 patients in the Xeljanz group are fixed.	Xeljanz group: Patients for whom at least Volume 1 is fixed at the specified timing. Control group: patients for whom at least Volume 1 is fixed at that timing.
5	Comparison of serious infection with control group	The timing at which 1-year data in all patients in Xeljanz group and control group are fixed.	All cases of Xeljanz and Control groups

\* The time of implementation will be decided based on the number of collected cases and duration.

At interim analyses, only the analyses of necessary items among statistical analyses specified in this plan will be performed. Items necessary for the interim analysis will be specified separately. At the final analysis, all analyses specified in this plan will be performed.

#### **4. HYPOTHESES AND DECISION RULES**

Since this survey is not a confirmatory study, statistical tests will be exploratory. Unless otherwise specified, tests will be 2-sided and the significance level will be 5%. A 2-sided confidence interval will be used for interval estimation, and the confidence coefficient will be 95%.

#### **5. ANALYSIS SETS**

##### **5.1. Safety Analysis Set**

###### **5.1.1. Safety analysis of the Xeljanz group**

- Safety analysis set

Of the enrolled patients with a scheduled observation period of 3 years and 6 months, those who have been confirmed to have received Xeljanz at least once are included. However, the following patients will be excluded from the safety analysis set.

- a. No CRF was collected (description in the report: "CRF not collected");
  - b. There was a violation or flaw of the contract (description in the report: "Violation/flaw of contract");
  - c. There was a violation in the enrollment process (description in the report: "Enrollment violation");
  - d. No information on the administration of survey drug was reported (description in the report: "No administration information");
  - e. No information on adverse events was reported (ie., existence or non-existence of adverse events is unidentifiable) - No visits after the initial prescription (description in the report: "No information on adverse events - No re-visits");
  - f. No information on adverse events was reported - Visits conducted after the initial prescription, but no record (description in the report: "No information on adverse events - No record").
- MTX adherent safety analysis set

The MTX adherent safety analysis set is defined as the patients with rheumatoid arthritis who have been poorly controlled if methotrexate (MTX) at a dose of more than 8 mg/week is continuously used for 3 months or longer among the new patients of the safety analysis set, that is described in the "Guidelines for the use of tofacitinib for all patients post-marketing surveillance".

The new patient is defined as the patients in which administration of Xeljanz was started for the first time after the registration of this surveillance in the Xeljanz group. In addition, the target patients with rheumatoid arthritis are 16 years old or older, and patients under 16 years old are excluded.

### **5.1.2. Comparison of the Xeljanz group and the control group**

- Comparative analysis set

Of the enrolled patients with a scheduled observation period of 3 years, those who were confirmed to treat Xeljanz in the Xeljanz group and a control drug (control drug is MTX, biological agents, DMARDs or immunosuppressive drug) at least once were included in the control group. The patients who apply to a to f in Section 5.1.1 are excluded.

The control group also excludes patients who do not meet the MTX criteria and patients who have been treated with Xeljanz.

- MTX adherent comparative analysis set

The MTX adherent comparative analysis set of the Xeljanz group is the patients who meets the MTX criteria among the new patients of the comparative analysis set.

As for the control group, since the comparative analysis set of the control group is limited to the patients who meet the MTX criteria, the same set is also used as the control group of MTX adherent comparative analysis set.

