##### [11] Laboratory tests (peripheral leukocyte count, peripheral lymphocyte count, $\beta$ -D-glucan)

2) Survey form

(1) Patient characteristics prior to and at the start of treatment

The following will be recorded for both treatment groups.

[1] Height/weight

[2] Inpatient/outpatient status

Indication (Patients with rheumatoid arthritis), stage and grade (Steinbrocker stage), and functional class (Steinbrocker functional class)

[3] Duration of disease

[4] Clinical history (past history and concurrent illness)

[5] History of smoking (history of smoking at treatment start)

[6] Family history of malignant tumor

(2) Previous treatment drugs for rheumatoid arthritis (3 months before treatment start)

The following will be recorded for both treatment groups.

[1] MTX

- Past use (presence/absence)
- Weekly dosage
- Duration of treatment

[2] Oral steroid use for rheumatoid arthritis

- Past use (presence/absence), period or treatment

[3] Tacrolimus

- Past use (presence/absence)
- Duration of treatment

(3) Dose record

[1] Xeljanz group

Number of doses per day, treatment period, reason for change (if there has been a change in administration)

[2] Control group

If there has been a switch to another type of pharmacotherapy, excluding Xeljanz, during the observation period, the case will be handled as a continued surveillance case, and the treatment record should be continuously entered.

In cases where Xeljanz has been administered, surveillance as a member of the control group will be handled as discontinued, and registration in the Xeljanz group will be necessary.

● MTX

Name of drug (name of product), weekly dosage, and duration of treatment

● Pharmacotherapy with drugs other than MTX (biological preparation, DMARDs, immunosuppressants, oral steroid preparations)

Name of drug (name of product), daily dosage (oral steroids), and duration of treatment

(4) Concomitant therapy (Xeljanz group)

For drug therapy, covering the period starting 3 months prior to the start of treatment in this Surveillance

and ending at the completion or discontinuation of the observation period will be completed. Medications used for the treatment of adverse events should also be recorded.

[Concomitant therapies coadministered with Xeljanz]

- [1] MTX
- [2] Biological preparations\*
- [3] DMARDs other than MTX and immunosuppressants\*
- [4] Oral steroid
- [5] Other drugs

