### 7.3 End-of-surveillance (discontinuation) record

Confirm whether or not treatment can be continued by Xeljanz or control group at end of observation period. If treatment by Xeljanz group or control group cannot be continued, write date of discontinuation and select item that corresponds to reason (multiple responses possible).

However, even if a switch to another type of pharmacotherapy, excluding Xeljanz, has been made in the control group after registration is complete, it will be handled as a continuing surveillance case, and if the pharmacotherapy has been discontinued, it will be handled as a surveillance discontinued case.

If adverse event or death is selected as the reason, the details thereof should be recorded in the adverse event section. [Also, for the control group, if the reason selected is associated with malignant tumor and death of patient (treatment start to 36 months) or serious infection (treatment start to Month 12 of treatment), the details thereof should be recorded].

 
[1] Remission
 
[2] Inadequate clinical response
 
[3] Adverse event
 
	} [1]-[3]: Subject to follow-up survey e)

 
[4] Death (date of death)
 
[5] No revisit
 
[6] Transfer to another hospital/department (name of hospital/department)
 
[7] Treatment with Xeljanz tablets (*Only applicable for the survey form for the control group)
 
	} [4]-[7]: End surveillance if any of the following apply

 
[8] Other
 
	

e) However, the observation period for subjects who correspond to "1) Xeljanz group (2) in 6.5 Observation period" will be only 6 months after the date of treatment start (Booklet 1) and no follow-up surveillance will be conducted.

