## 7.7 Follow-up

In cases that discontinued (excluding those where the reason for discontinuation was "death of patient," "did not return to hospital," or "transferred to another hospital/department"), a follow-up survey will be conducted on information related to the drug administration conditions after discontinuation and adverse events (serious infections (12 months), malignant tumors, adverse events leading to death) for a period of 3 years after the date of treatment start, if possiblef. If the subject is lost to follow up, follow-up survey will not be required.

f) However, the observation period for subjects who correspond to "1) Xeljanz group (2) in 6.5 Observation period" will be only 6 months after the date of treatment start (Booklet 1) and no follow-up survey will be conducted.

For cases that discontinued in the 24-month period following treatment start (booklets 1 to 3), information from the date of discontinuation onward should be written on the follow-up survey form issued by the sponsor. Cases discontinuing during the observation period from treatment start to the 25th month after (booklet 4) should be confirmed in the reinvestigation of information from the date of discontinuation onward for the period from treatment start to 36 months after.

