**Table 2. Categories of Tabulation Items for Discontinuation and Dropout**

Item	Category
Reason for discontinuation	Remission (Xeljanz group only), inadequate clinical effect (Xeljanz group only), adverse events (Xeljanz group only), death of patient, no revisits, transfer to other hospitals and departments, administration of Xeljanz Tablets (survey the control group only), others
Number of days to discontinuation	Start of treatment - 1 month (Day 1 to Day 31), 1 month < - 3 months (Day 32 to Day 92), 3 months < - 6 months (Day 93 to Day 184), 6 months < - 9 months (Day 185 to Day 275), 9 months < - 12 months (Day 276 to Day 366), 12 months < - 18 months (Day 367 to Day 549), 18 months < - 24 months (Day 550 to Day 731), 24 months < - 30 months (Day 732 to Day 914), 30 months < - 36 months (Day 914 to Day 1096), >36 months (Day 1097-)

- Lists of excluded patients**

Patients excluded from the safety analysis set, patients excluded from the subpopulation that meets the MTX criteria, patients excluded from the efficacy analysis set, and reasons for exclusion will be listed.

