**Table 5. Definitions in the Comparison of Malignant Tumors**

Term	Definition
Patients without malignant tumors	Patients who do not correspond to the each definition of patients with malignant tumors
Time to malignant tumor during overall observation period	Date of the development of malignant tumor - date of the initiation of treatment + 1
Censoring period for patients without malignant tumors during overall observation period	Date of completion or discontinuation of follow-up - date of the initiation of treatment + 1
Time to malignant tumor during treatment period	Date of the development of malignant tumor - date of the initiation of treatment + 1
Censoring period for patients without malignant tumors (treatment period)	Date of the completion of treatment - date of the initiation of treatment+ 1
Time to malignant tumor during the treatment period (+28 days)	Date of the development of malignant tumor - date of the initiation of treatment + 1
Censoring period for patients without malignant tumors during the treatment period (+28 days)	Date of the completion of treatment + 28- date of the initiation of treatment + 1

• **Development of malignant tumors**

The number of malignant tumors in each group and the proportion of occurrence are calculated for each SOC and PT. Furthermore, it is calculated for each cancer type (stomach, lung, breast, cervix, uterine body, ovary, malignant lymphoma, large intestine, pancreas, bladder, kidney / urinary tract (excluding bladder), other). Females are targeted for malignant tumors of the breast, cervix, uterine body and ovaries.

• **Incidence rate of malignant tumors**

The number of patients with malignant tumors in each group, incidence rate, and the 95% confidence interval will be calculated in accordance with [Section 8.1.5](#).

In addition, the incidence ratio between treatment groups and the 95% confidence interval and the difference in incidence rate between treatment groups and the 95% confidence interval will be calculated.

For covariates concerning malignant tumors (Section 6.3), incidence by single factor will be calculated, and the pooled incidence ratio and the 95% confidence interval and the pooled difference in incidence rate and the 95% confidence interval will be calculated.

• **Incidence proportion of malignant tumors**

The number of patients with malignant tumors in each group, the incidence proportion, and the 95% confidence interval will be calculated in accordance with [Section 8.1.5](#).

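### Handling of controls who later start Xeljanz is not settled: protocol 7.3 and 7.7 conflict, the SAP 5.1.2 exclusion is undated, and SAP Tables 5–7 set no stop at the first Xeljanz dose

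*SAP*

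**What the plan says.** **End at the switch.** In the control-group dose record of protocol 7.1: "In cases where Xeljanz has been administered, surveillance as a member of the control group will be handled as discontinued". The same sentence requires registration in the Xeljanz group. Protocol 7.3 lists as a discontinuation reason "Treatment with Xeljanz tablets (*Only applicable for the survey form for the control group" and places it in the block marked "4]-[7]: End surveillance if any of the following apply". Only remission, inadequate response and adverse event are marked for the follow-up survey.

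**Follow-up to 3 years.** Protocol 7.7 sends discontinued cases to follow-up for malignant tumors and death until 3 years after treatment start, where possible, "excluding those where the reason for discontinuation was 'death of patient,' 'did not return to hospital,' or 'transferred to another hospital/department". Starting Xeljanz is not among those exemptions. Protocol 6.5 [4] has no such exemption either.

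**Censoring.** For the primary malignancy window, SAP Table 5 sets the censoring period of event-free patients as "Date of completion or discontinuation of follow-up - date of the initiation of treatment + 1". Neither this table nor Tables 6 and 7 mentions the first Xeljanz dose.

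**Analysis set.** SAP 5.1.2 states: "The control group also excludes patients who do not meet the MTX criteria and patients who have been treated with Xeljanz". No time reference is given. SAP Table 2 nevertheless tabulates, as a reason for discontinuation, "administration of Xeljanz Tablets (survey the control group only), others".

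**Two registrations.** Protocol 6.4 requires a control given Xeljanz during the registration period to be registered in the Xeljanz group as well; protocol 7.1 sets no such time limit. SAP 5.2 treats several identifiers as one patient only where they arose from a transfer of hospital or department.

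**The concern.** These patients cross between the two groups whose malignancy and serious-infection rates the surveillance sets out to compare. For a control who starts Xeljanz at Month 12, the documents allow three outcomes:

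- control time ends at Month 12 (7.1 and 7.3);
- control time runs on to Month 36 while the patient takes Xeljanz (7.7 with Table 5);
- the whole control record is removed (5.1.2 read literally at the data cut).

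Removal selects controls on a treatment they receive later. The person-time removed is event-free by construction, so the control rate rises and the ratio falls. Running on credits tumors that arise on Xeljanz to the control group. If the true ratio exceeds 1, both make Xeljanz look safer, which is the wrong direction for a safety comparison. The choice would also be left to the analyst after the data are in.

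**Working it through.** **Inputs from the documents** (protocol 3, rationale for sample size): malignancy rate 1.16 per 100 patient-years, taken as equal in both groups; about 50% dropout by 3 years; 4000 Xeljanz patients and 2000 controls.

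**Assumptions.** The documents give no control-to-Xeljanz switch rate. I used s = 5, 10, 20 and 30% by 3 years in the absence of dropout, a constant switching hazard unrelated to risk, and true Xeljanz/control rate ratios R of 1, 1.5 and 2.

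**1. The plan's own figure.** Linear dropout to 50% gives a mean of 3 × (1 + 0.5)/2 = 2.25 years. Then 4000 × 2.25 × 0.0116 = 104.4, against 104 stated, so the basis is reproduced. For controls, 2000 × 2.25 = 4500 patient-years and 4500 × 0.0116 = 52.2 events.

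**2. Precision.** With the standard error used in SAP 8.1.6, √(1/104.4 + 1/52.2) = 0.170. The 95% confidence factor is exp(1.96 × 0.170) ≈ 1.39.

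**3. Model.** N = 2000, λ = 0.0116, retention S(t) = 1 − t/6, switching hazard σ = −ln(1 − s)/3, all integrals over 0 to 3 years.

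- A, end at switch: PT_A = N∫S(t)e^(−(σ+λ)t)dt; events D = λ·PT_A; rate = λ.
- B, follow as control: add post-switch time PT_post with event rate Rλ; rate = (D + Rλ·PT_post)/(PT_A + PT_post).
- C, delete switchers: remove their pre-switch time PT_sw = N∫tσS(t)e^(−(σ+λ)t)dt, which carries no events; rate = D/(PT_A − PT_sw).

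The ratio obtained is Rλ divided by the control rate.

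**4. Numbers for C** (rates per 100 patient-years).

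- s = 10%: about 149 observed switchers; 49.09/(4231.6 − 193.2) = 1.215; at R = 1 the ratio is 1.16/1.215 = 0.95.
- s = 20%: about 299 observed switchers; 46.67/(4023.2 − 380.6) = 1.281; at R = 1 the ratio is 1.16/1.281 = 0.91.

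**5. Numbers for B at R = 2.**

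- s = 10%: (49.09 + 4.58)/(4231.6 + 197.4) = 1.212; 2.32/1.212 = 1.92 (1.915 before rounding).
- s = 20%: (46.67 + 9.36)/(4023.2 + 403.5) = 1.266; 2.32/1.266 = 1.83.

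**6. Ratio obtained** (A returns the true value throughout)

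| Switching | R=1: B | R=1: C | R=1.5: B | R=1.5: C | R=2: B | R=2: C |
|---|---|---|---|---|---|---|
| 5% | 1.00 | 0.98 | 1.48 | 1.47 | 1.96 | 1.96 |
| 10% | 1.00 | 0.95 | 1.47 | 1.43 | 1.92 | 1.91 |
| 20% | 1.00 | 0.91 | 1.43 | 1.36 | 1.83 | 1.81 |
| 30% | 1.00 | 0.85 | 1.40 | 1.28 | 1.75 | 1.71 |

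**7. Scale.** Under C at R = 1, the shift in the log ratio relative to the standard error of 0.170 is 0.022/0.170 = 0.13 at 5% switching, 0.047/0.170 = 0.28 at 10%, 0.100/0.170 = 0.59 at 20%, and 0.159/0.170 = 0.94 at 30%.

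**8. Serious infection.** The primary window is treatment plus 28 days, capped at 1 year (SAP 8.2.3.1.2 and Table 6). The 3-year follow-up question hardly touches it, but the 28 days after a switch can still place early Xeljanz time in the control group. I did not put a number on this.

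**The case against.** A reader might infer that the documents lay down three incompatible rules. They do not.

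- **The SAP exclusion is more naturally an entry criterion.** It stands beside the MTX criteria, which apply at entry, and it echoes protocol 2 and 6.4 (no previous Xeljanz) and SAP 2.1 (Xeljanz-naive controls). Table 2 expects later switchers among the controls. Read this way it agrees with 7.3. This stands: deletion is a risk created by an undated sentence, not a stated rule.
- **Protocol 7.7 reaches switchers only by omission.** Protocol 7.1 and 7.3 are explicit, and the Table 5 end of follow-up can be read as the switch date. Nothing in 7.7 says that switchers continue as controls. This also stands, but the contradiction between 7.3 and 7.7 remains.

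Other stronger readings also go too far.

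- **That following switchers as controls is always biased.** At the plan's assumption of equal rates it gives 1.00. It resembles a comparison by initial treatment, since Xeljanz patients are themselves followed after stopping.
- **That every post-switch tumor is counted twice.** The comparative set takes only patients scheduled for 3 years. Xeljanz patients registered after that cohort closes are followed for 6 months and fall outside it (protocol 6.5, SAP 5.1.2). Dual membership is limited to switchers who enter the 3-year Xeljanz cohort.
- **That no sensitivity analysis exists.** The SAP revision history places the sensitivity analyses for this comparison in 8.2.3.1.4, and that text is redacted.

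Finally, SAP section 4 makes all tests exploratory, and ending at the switch is not automatically unbiased. It assumes non-informative switching and is asymmetric with the Xeljanz group's follow-up after discontinuation.

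**Conclusion.** The point holds as a gap that should be fixed, with moderate confidence. Protocol 7.3 and 7.7 contradict each other for control switchers, SAP 5.1.2 is undated, and SAP Tables 5–7 do not state where a switcher's control time ends. Re-registered switchers in the 3-year Xeljanz cohort can belong to both groups, and no linkage rule is stated beyond transfers.

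The size depends on the assumed switch rate and on switching being unrelated to risk. At 10–20% switching the shifts are those given for B and C in the table. Literal exclusion biases the ratio downward even when there is no true difference; following switchers as controls does so only when the true ratio exceeds 1. Set against the precision of the comparison, the effect is small at 5–10% switching and material at 20–30%. The documents do not support treating deletion of switchers as the intended analysis.

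**What to change.** 1. **SAP 5.1.2:** limit the exclusion to patients treated with Xeljanz before the start date of surveillance.
2. **Protocol 7.7:** reconcile with 7.3 by adding treatment with Xeljanz (control group) to the reasons exempt from control follow-up.
3. **SAP Tables 5–7:** for controls who start Xeljanz, end control time the day before the first Xeljanz dose, including within the 28-day extension. Count later events and time only in the Xeljanz group, and only if the patient qualifies there.
4. **Dual registration:** link the two registration IDs and use a variance clustered on patient in the Cox and IPTW models.
5. **Sensitivity analysis:** add one that does not rely on non-informative switching, for example inverse-probability-of-censoring weights, unless the redacted section 8.2.3.1.4 already has it.

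**Cost:** a few words in the SAP and one phrase in protocol 7.7, plus the ID linkage and one extra analysis. Control treatment records are already collected, and starting Xeljanz is already recorded as a dated discontinuation.
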